6.2. General Considerations

Statistical analysis of this study will be the responsibility of Eli Lilly and Company (Lilly) or its designee. Some analyses and summaries described in this analysis plan may not be conducted if not warranted by data (for example, few events to justify conducting an analysis). Additional analyses of the data may be conducted as deemed appropriate.

Unless otherwise noted, tests of treatment effects will be conducted at a 2-sided alpha level of 0.05, and the confidence interval (CI) will be calculated at 95% 2-sided.

Unless specified otherwise, efficacy and safety will be assessed using the modified intention-to-treat (mITT) population, and data will be analyzed based on the randomized treatment (that is, not the actual treatment received by the participant). For submission of Study GPHK to the US Food and Drug Administration (FDA) to support the registration of tirzepatide for chronic weight management, the primary efficacy analysis will be conducted using Full Analysis Set (FAS). For other purposes, the efficacy analysis will be conducted using Efficacy Analysis Set (EAS). Safety analysis will be conducted using Safety Analysis Set (SS).

Summary descriptive statistics for continuous measures will include sample size, mean, standard deviation (SD), median, minimum, and maximum. The analysis model to make comparisons among treatment groups relative to continuous measurements assessed over time will be either analysis of covariance (ANCOVA) or a mixed model for repeated measures (MMRM).

Kaplan-Meier method will be used for estimation of cumulative event-free survival rates over time, and Cox proportional hazards regression analysis will be used to compare hazards rates among treatments.

Summary statistics for categorical measures (including categorized continuous measures) will include sample size, frequency, and percentages. Logistic regression will be used to examine the treatment difference in binary efficacy outcomes if there is a need to adjust for covariate. Otherwise, Fisher’s exact test will be used to examine the treatment difference.

Summary statistics for discrete count measures will include sample size, mean, SD, median, minimum, and maximum.

Unless specified otherwise, baseline will be defined as the last available non-missing measurement during Visit 1 to Visit 3. For the safety related parameters, the definition of baseline and postbaseline are specified in [Table GPHK.6.2](#).

Table GPHK.6.2. Baseline and Postbaseline Definitions for Safety Groups

Analysis Set	Analysis Type	Baseline	Postbaseline
SS	1.1) Treatment-Emergent Adverse Events	The baseline period is defined as the start of screening and ends prior to the first dose of study treatment (typically at Week 0).	Starts after the first dose of study treatment and ends at the end of the study period (including off-drug follow up visit).
SS	1.2) Treatment-Emergent Abnormal Labs ^a , Vital Signs, and ECGs.	Baseline will include all scheduled and unscheduled measurements during the baseline period (Visit 1 to Visit 3)	Postbaseline will be defined as measurements after Visit 3 . All scheduled and unscheduled measurements will be included.
SS	1.3) Change from Last Baseline to Week xx and to Last Postbaseline for Labs ^a , Vital Signs, and ECGs.	The last scheduled and unscheduled non-missing assessment recorded during the baseline period defined above (1.2).	Postbaseline will be defined as above (1.2). Only scheduled visits will be included. The early discontinuation (ED) visits are considered scheduled visits.

Abbreviations: ECGs = electrocardiogram; SS = Safety Analysis Set.

^a Immunogenicity related analysis is specified in Section [6.14.3.7](#).

There will be 2 estimands of interest in evaluating primary and key secondary efficacy objectives:

- For objectives controlled for Type 1 error at 72 weeks:
 - the “efficacy” estimand, defined as the average treatment effect of tirzepatide relative to placebo at 72 weeks, as an adjunct to a reduced-calorie diet and increased physical activity, in the randomized participants had they remained on their randomized treatment for the entire planned 72 weeks treatment duration.
 - the “hybrid” estimand, is the average treatment effect of tirzepatide relative to placebo at 72 weeks, as an adjunct to a reduced-calorie diet and increased physical activity, for the randomized participants regardless of the adherence to treatment

- For objectives controlled for Type 1 error assessed after 72 weeks:
 - the “efficacy” estimand, defined as the treatment effect of tirzepatide relative to placebo at 176/193 weeks, as an adjunct to a reduced-calorie diet and increased physical activity, in the randomized participants with prediabetes at randomization had they remained on their randomized treatment for the entire planned 176 weeks treatment duration.
 - the “hybrid” estimand, is the average treatment effect of tirzepatide relative to placebo at 176/193 weeks, as an adjunct to a reduced-calorie diet and increased physical activity, for the randomized participants with prediabetes at randomization regardless of the adherence to treatment

End of study participation for a participant will be the earliest of date of death, date of withdrawal from further participation in the study, or date of safety follow-up visit (Visit 801 or Visit 802). For participants considered to be lost-to-follow-up, end of study participation will be the date of lost-to-follow-up reported by the investigator. Participant data included in the database after the last date of study participation (including safety follow-up period) will be excluded from statistical analysis.

Statistical treatment comparisons will only be performed between tirzepatide and placebo. Since the trial is not adequately powered to detect difference among tirzepatide doses, comparisons among tirzepatide doses will not be performed unless otherwise specified.

Statistical summaries and results of statistical analyses will be displayed in the following order: Placebo, tirzepatide 5 mg, tirzepatide 10 mg, tirzepatide 15 mg, and pooled tirzepatide (10 mg and 15 mg, or all doses combined, if necessary).

Not all analyses described in this SAP will necessarily be included in the Clinical Study Reports (CSRs). Any analysis described in this SAP and not provided in the CSR would be available upon request. Not all displays will necessarily be created as a “static” display. Some may be incorporated into interactive display tools instead of or in addition to a static display.

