1.3.1. Schedule of Activities covering visits to primary study endpoint

Visit*	1	2	3*	4	5	6	7	8	9	10	11	12	13	14	15	16	17	18	19	20	21	99*	ED*	801*		
Week of Treatment	-2	-1	0	4	8	12	16	20	24	28	32	36	40	44	48	52	56	60	64	68	72	72			4 wks Post TxP	
Allowable Deviation (days)*		±3	±3	±3	+7	±3	+7	±3	±3	±3	±3	+7	±3	±3	±3	±3	±3	±3	±3	±3	±7	±7			±3	
Fasting Visit*	X	X	X	X	X	X	X	X	X			X			X			X			X	X	X		X	
Telephone Visit										X	X		X	X		X	X		X	X						
Informed consent	X																									
Randomization			X																							
Register study visit in IWRS	X	X	X	X	X	X	X	X	X	X	X	X	X	X	X	X	X	X	X	X	X	X	X	X	X	
Clinical Assessments																										
Medical history*	X																									
Physical examination	X																									
Height	X																									
Weight*	X		X	X	X	X	X	X	X			X			X			X			X	X	X		X	
Waist circumference			X	X	X	X	X	X	X			X			X			X			X	X	X		X	
Electrocardiogram*			X	X	X	X	X	X	X			X									X		X		X	
Vital signs (3 sitting BP and HR)*	X		X	X	X	X	X	X	X			X			X			X			X		X		X	
Adverse events and product complaints	X	X	X	X	X	X	X	X	X	X	X	X	X	X	X	X	X	X	X	X	X	X	X	X	X	X
Concomitant medications	X	X	X	X	X	X	X	X	X	X	X	X	X	X	X	X	X	X	X	X	X	X	X	X	X	X
Participant Education and Assessment																										
Hand out diary, instruct in use*			X		X			X			X			X			X			X						

Visit*	1	2	3*	4	5	6	7	8	9	10	11	12	13	14	15	16	17	18	19	20	21	99*	ED*	801*
Week of Treatment	-2	-1	0	4	8	12	16	20	24	28	32	36	40	44	48	52	56	60	64	68	72	72		4 wks Post TxP
Allowable Deviation (days)*		±3	±3	±3	+7	±3	+7	±3	±3	±3	±3	+7	±3	±3	±3	±3	±3	±3	±3	±3	±7	±7		±3
Fasting Visit*	X	X	X	X	X	X	X	X	X			X			X			X			X	X	X	X
Telephone Visit										X	X		X	X		X	X		X	X				
Review study participant diary, including study-drug compliance*				X	X	X	X	X	X	X	X	X	X	X	X	X	X	X	X	X	X	X		X
Lifestyle Program instructions*			X	X	X	X			X			X			X			X			X		X	
Review diet and exercise goals*			X	X	X	X	X	X	X	X	X	X	X	X	X	X	X	X	X	X	X	X		X
Injection training with autoinjector demonstration device*			X																					
Dispense study drug			X	X	X	X	X	X	X			X			X			X			X*			
Observe participant administer study drug*			X																					
Participant returns study drugs and injection supplies				X	X	X	X	X	X			X			X			X			X		X	
Laboratory Tests																								
Serum pregnancy test*	X																							
Urine pregnancy test*			X			X			X			X			X			X			X	X	X	
Follicle-stimulating hormone test*	X																							

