Visit*	1	2	3*	4	5	6	7	8	9	10	11	12	13	14	15	16	17	18	19	20	21	99*	ED*	801*
Week of Treatment	-2	-1	0	4	8	12	16	20	24	28	32	36	40	44	48	52	56	60	64	68	72	72		4 wks Post TxP
Allowable Deviation (days)*		±3	±3	±3	+7	±3	+7	±3	±3	±3	±3	+7	±3	±3	±3	±3	±3	±3	±3	±3	±7	±7		±3
Fasting Visit*	X	X	X	X	X	X	X	X	X			X			X			X			X	X	X	X
Telephone Visit										X	X		X	X		X	X		X	X				
2-hour oral glucose tolerance test (includes glucose, insulin, c-peptide at each timepoint)*		X																			X		X	
Chemistry panel (include Cr for eGFR calculation and glucose)*	X		X			X			X			X			X			X			X		X	X
Lipid panel	X		X						X												X		X	X
Fasting insulin						X			X			X			X			X			X		X	X
C-peptide						X			X			X			X			X			X		X	X
Free fatty acids	X		X						X												X		X	X
Urinary albumin/creatinine	X*								X												X		X	X
Cystatin-c	X*								X												X		X	X
Calcitonin	X*					X			X												X		X	X
Hematology	X*					X			X												X		X	X
HbA1c	X		X			X			X			X			X			X			X		X	X
Pancreatic amylase, lipase	X		X			X			X												X		X	X
Thyroid-stimulating hormone	X*																							
Immunogenicity (includes PK sample)*			X	X		X			X						X						X		X	X
TZP PK*					X		X					X												
Pharmacogenetic stored sample			X																					

Visit*	1	2	3*	4	5	6	7	8	9	10	11	12	13	14	15	16	17	18	19	20	21	99*	ED*	801*
Week of Treatment	-2	-1	0	4	8	12	16	20	24	28	32	36	40	44	48	52	56	60	64	68	72	72		4 wks Post TxP
Allowable Deviation (days)*		±3	±3	±3	+7	±3	+7	±3	±3	±3	±3	+7	±3	±3	±3	±3	±3	±3	±3	±3	±7	±7		±3
Fasting Visit*	X	X	X	X	X	X	X	X	X			X			X			X			X	X	X	X
Telephone Visit										X	X		X	X		X	X		X	X				
Nonpharmacogenetic stored sample			X			X			X						X						X		X	X
Mental Health Questionnaires																								
PHQ-9*	X		X			X			X			X			X			X			X	X	X	X
C-SSRS (Baseline/Screening Version)*	X																							
C-SSRS (Since Last Visit Version)*		X	X	X	X	X	X	X	X	X	X	X	X	X	X	X	X	X	X	X	X	X	X	X
Self-Harm Supplement Form*	X	X	X	X	X	X	X	X	X	X	X	X	X	X	X	X	X	X	X	X	X	X	X	X
Self-Harm Follow-up Form*	X	X	X	X	X	X	X	X	X	X	X	X	X	X	X	X	X	X	X	X	X	X	X	X
Patient Reported Outcomes																								
PGIS			X																			X	X	
SF-36, version 2, acute form			X																			X	X	
IWQOL-Lite CT			X																			X	X	
EQ-5D-5L			X																			X	X	

1.3.2. Schedule of Activities for additional 2-year treatment period for participants with prediabetes at randomization

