Visit*	101	102	103	104	105	106	107	108	109	110	111	112	113	114	115	116	199*	ED*	802*
Week of Treatment	78	85	91	98	104	111	117	124	130	137	143	150	156	163	169	176	176		17 wks Post TxP
Allowable Deviation (days)*	±7	±7	±7	±7	±7	±7	±7	±7	±7	±7	±7	±7	±7	±7	±7	±7	±7		±3
Fasting Visit*		X		X		X		X		X		X		X		X	X	X	X
Telephone Visit	X		X		X		X		X		X		X		X				
C-SSRS (Since Last Visit Version)*	X	X	X	X	X	X	X	X	X	X	X	X	X	X	X	X	X	X	X
Self-Harm Supplement Form*	X	X	X	X	X	X	X	X	X	X	X	X	X	X	X	X	X	X	X
Self-Harm Follow-up Form*	X	X	X	X	X	X	X	X	X	X	X	X	X	X	X	X	X	X	X
PROs																			
PGIS								X								X		X	
SF-36, version 2 acute								X								X		X	
IWQOL-Lite -CT								X								X		X	
EQ-5D-5L								X								X		X	

*Please see table below for corresponding additional information

Abbreviations: BP = blood pressure; Cr= creatinine; C-SSRS = Columbia-Suicide Severity Rating Scale; ED= early discontinuation of treatment; eGFR = estimated glomerular filtration rate; HbA1c = hemoglobin A1c; HR = heart rate; IWQOL-Lite-CT = Impact of Weight on Quality of Life-Lite Clinical trials; IWRS = interactive web-response system; PGIS = Patient Global Impression of status for physical activity; PHQ-9 = Patient Health Questionnaire-9; PK = pharmacokinetics; SF-36 = Short-Form-36 Health Survey version 2, acute form; TxP = treatment period; TZP = tirzepatide

Additional Information Regarding Activities Described in Schedule of Activities

Activity	Notes
Visit Fasting Visit	On all office visits, study participants should be reminded to report to the site before taking study drug (s) in a fasting condition, after a period of approximately 8 hours without eating, drinking (except water), or any significant physical activity. Since some screening procedures need to be completed in the fasting state, Visit 1 may be conducted over more than 1 day to ensure necessary conditions are met.
Visit 3	Baseline assessments must be completed before processing in the IWRS.

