6.3. Adjustments for Covariates

The study is stratified by prediabetes status at randomization, country, and sex (female, male). Where necessary to be included as a stratification factor, countries with fewer than 10 randomized participants will be pooled into 1 category (pooled country).

Unless otherwise specified, for efficacy related analyses at 72 weeks, country/pooled country, sex, prediabetes status at randomization and corresponding baseline value will be used as a covariate. For efficacy analyses at 176 weeks (or 193 weeks), country/pooled country, sex and corresponding baseline value will be used as a covariate.

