6.13.2. Secondary Efficacy Analyses Subject to Type 1 Error Rate Control

Table GPHK.6.4. Secondary Measures Controlled for Type 1 Error

Objectives	Relative to the efficacy measure:	Analysis conducted in a manner similar to	Additional Information
Tirzepatide 10 mg and 15 mg combined is superior to placebo:	Mean change in body weight (kg) from randomization at 20 weeks	MMRM model in Section 6.13.1.1 for efficacy estimand and ANCOVA model in Section 6.13.1.2 for hybrid estimand	
Tirzepatide 5 mg is superior to placebo:	Mean percent change in body weight from randomization and percentage of participants achieving at least 5% body weight reduction at 72 weeks	Section 6.13.1.1 for efficacy estimand and Section 6.13.1.2 for hybrid estimand	
Tirzepatide 10 mg and/or 15 mg is superior to placebo:	Percentage of participants achieving body weight reduction $\geq 10\%$, $\geq 15\%$ and $\geq 20\%$ at 72 weeks	logistic model in Section 6.13.1.1 for efficacy estimand and logistic model in Section 6.13.1.2 for hybrid estimand	
	Mean change in waist circumference (cm) from randomization at 72 weeks	MMRM model in Section 6.13.1.1 for efficacy estimand and ANCOVA model in Section 6.13.1.2 for hybrid estimand	LSM estimates will be plotted by treatment through 72-weeks.

Secondary Measures Controlled for Type 1 Error

Objectives	Relative to the efficacy measure:	Analysis conducted in a manner similar to	Additional Information
Tirzepatide 10 mg and 15 mg combined is superior to placebo	Mean change in SF-36 v2 acute form Physical Functioning domain score from randomization at 72 weeks	ANCOVA model with the terms of treatment group, stratification factors as fixed effects, and baseline SF-36 v2 acute form Physical Functioning domain score as a covariate.	For efficacy estimand, missing data will be imputed based on LOCF method. For hybrid estimand, missing data will be imputed based on Section 6.13.1.3.
Tirzepatide (all doses combined) is superior to placebo:	Mean change in triglycerides, HDL-C, non-HDL-C, SBP and fasting insulin from randomization at 72 weeks	MMRM model in Section 6.13.1.1 for efficacy estimand and ANCOVA model in Section 6.13.1.2 for hybrid estimand	For hybrid estimand, missing data will be imputed first for each treatment based on Section 6.13.1.3, then combine all tirzepatide doses.

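### SBP and lipids are measured at both Visit 1 and Visit 3, but the models adjust only for the last value; adding the Visit 1 value as a second covariate would modestly narrow the intervals of four type-1-error-controlled endpoints

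*SAP*

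**What the plan says.** The Schedule of Activities (Protocol 1.3.1) has the rows "Vital signs (3 sitting BP and HR)* X X" and "Lipid panel X X"; the first two marks in each fall under Visit 1 (week -2) and Visit 3 (week 0). The chemistry panel, under which Protocol 10.2 lists triglycerides and total cholesterol, is drawn at the same two visits. Visit 1 is a fasting visit, and the notes to the schedule add that "Visit 1 may be conducted over more than 1 day to ensure necessary conditions are met", so the two lipid samples are comparable.

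SAP 6.2 sets the baseline rule: "baseline will be defined as the last available non-missing measurement during Visit 1 to Visit 3". Protocol 9.4.1 has the same definition. For efficacy analyses at 72 weeks, SAP 6.3 says that "country/pooled country, sex, prediabetes status at randomization and corresponding baseline value will be used as a covariate".

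Table GPHK.6.4 in SAP 6.13.2 lists "Mean change in triglycerides, HDL-C, non-HDL-C, SBP and fasting insulin from randomization at 72 weeks" among the measures under type 1 error control. The comparison is all tirzepatide doses combined against placebo, by MMRM for the efficacy estimand and by ANCOVA with multiple imputation for the hybrid estimand.

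When a Visit 3 value exists, no efficacy model uses the Visit 1 value. It enters only as the fallback when Visit 3 is missing, and in the safety summaries of treatment-emergent abnormalities (Table GPHK.6.2, row 1.2).

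**The concern.** SBP and lipids vary from visit to visit, so the Visit 3 value is an imperfect measure of a participant's usual level. A second pre-randomization value about two weeks earlier carries further information on that level. Leaving it out makes the residual variance larger than it need be, which gives wider intervals and lower power for H_p,7 to H_p,10.

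Four endpoints are affected, not five. Fasting insulin is in the same pooled family but has no scheduled draw at Visit 1 or Visit 3. Its only scheduled pre-dose value comes from the Visit 2 glucose tolerance test.

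**Working it through.** **What the plan gives.** Protocol 9.2 states no power, SD or correlation for SBP or lipids, so there is no figure of the plan's own to reproduce for these endpoints. As a calibration only: for percent weight change, 600 × (1 − 0.25) = 450 per arm, a difference of 11, SD 10 and two-sided alpha 0.025 give power above 0.999. This agrees with the stated figure of more than 90%.

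**Inputs.** The pooled comparison randomizes 1800 against 600. Applying the same 25% dropout gives 1350 against 450. Let r be the Visit 1 to Visit 3 correlation and rho the correlation of either baseline with Week 72. Both are assumptions.

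**Formulas** (SD units, complete-data ANCOVA, both baselines equally correlated with Week 72):

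- Visit 3 alone as covariate: residual variance 1 − rho².
- Visit 3 and Visit 1 as two covariates: 1 − 2rho²/(1 + r).
- Interval width ratio: square root of the second over the first. Equivalent gain in participants: the first over the second, minus 1.

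**One case in full, r = 0.7, rho = 0.5.** Unadjusted half-width: 1.96 × √(1/450 + 1/1350) = 0.1067 SD. Planned: 0.1067 × √0.75 = 0.0924. With Visit 1 added: 1 − 0.5/1.7 = 0.706, and 0.1067 × √0.706 = 0.0896. The interval is 3.0% narrower, equal to 0.75/0.706 − 1 = 6.2% more participants.

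| r | rho | Planned variance | Two covariates | CI narrower | Equivalent extra N |
|---|---|---|---|---|---|
| 0.6 | 0.4 | 0.840 | 0.800 | 2.4% | 5.0% |
| 0.7 | 0.5 | 0.750 | 0.706 | 3.0% | 6.2% |
| 0.8 | 0.6 | 0.640 | 0.600 | 3.2% | 6.7% |
| 0.8 | 0.7 | 0.510 | 0.456 | 5.5% | 12.0% |
| 0.8 | 0.4 | 0.840 | 0.822 | 1.1% | 2.2% |
| 0.7 | 0.7 | 0.510 | 0.424 | 8.9% | 20.4% |

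The first four rows take r above rho by 0.1 or 0.2. The fifth shows a wide gap and the last the best case, r = rho. Over r from 0.5 to 0.9 and rho from 0.3 to 0.7, with rho no larger than r, the gain runs from 0.3% to 8.9%.

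**If Visit 1 predicts Week 72 less well than Visit 3.** At r = 0.7 and a Visit 3 correlation of 0.5, a Visit 1 correlation of 0.425 gives 0.7%. At 0.35 (= 0.7 × 0.5) the gain is zero, because Visit 1 then adds nothing once Visit 3 is known.

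**Simulation.** ANCOVA of change from Visit 3, 1350 against 450, 1000 runs for each of the first four rows. The interval was narrower in every run, with mean width ratios 0.976, 0.970, 0.969 and 0.945. Type I error with the second covariate was 0.044 to 0.052. The cost is one of about 1,790 residual degrees of freedom.

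**Two-visit mean as sole covariate.** With change from Visit 3 as the response, half the Visit 3 minus Visit 1 difference stays in the residual. It has variance (1 − r)/2, so residual variance is 1 − 2rho²/(1 + r) + (1 − r)/2:

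- r = rho = 0.5: 0.917 against 0.750 as planned, interval 11% wider.
- r = rho = 0.6: 0.750 against 0.640, 8% wider.
- r = rho = 0.7: 0.574 against 0.510, 6% wider.
- r = 0.8, rho = 0.6: 0.700 against 0.640, √(0.700/0.640) = 1.046, so 5% wider.

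It exceeds 1 − rho² whenever rho² is below (1 + r)/2, which always holds for rho ≤ r < 1.

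**The case against.** The strongest case against acting is that this is a preference. The baseline rule is pre-specified identically in both documents, and the analysis is valid. The comparison is large: with rho = 0.5 the planned model already has 90% power at alpha 0.05 for about 0.15 SD. No SBP or lipid effect size is given, so no conclusion is shown to be at risk. That stands, and it keeps the point at the level of an optional improvement. Equally, Protocol 9.2 does not show that precision for these endpoints is already ample.

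Second, a reader might infer that baseline SBP is a single noisy reading. It is not: three sitting measurements are taken per visit, and SAP 6.14.4 averages records from the same visit. That removes within-visit noise but not visit-to-visit variation, and no within-visit replicate is scheduled for lipids. This may reduce the gain for SBP without removing it.

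Third, the change is not wholly free under the hybrid estimand. SAP 6.13.1.3 imputes from retrieved dropouts in the same arm, possibly a small group, and switches to placebo-based imputation if the model does not converge. Another term adds some strain there; leaving it out would mismatch the imputation and analysis models. The formulas and simulation above cover complete-data ANCOVA, with neither imputation nor MMRM. This calls for a line of specification and some caution about the exact gain.

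**Conclusion.** The point holds as a modest loss of efficiency. Under the assumptions above, the intervals for SBP, triglycerides, non-HDL-C and HDL-C could be about 2 to 6% narrower, equal to about 5 to 12% more participants, for r of 0.6 to 0.8 with rho of 0.4 to 0.7 somewhat below r. Wider gaps between r and rho give less, about 1% at r = 0.8 and rho = 0.4. The direction is firm unless Visit 1 adds nothing beyond Visit 3; the size depends on correlations that blinded data could supply.

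Two stronger readings are not supported. A reader might infer a general gain of 6 to 9%, or 12 to 20% more participants. That requires r = rho between 0.5 and 0.7: readings about two weeks apart correlating no better than readings 72 weeks apart across treatment. Nothing in the documents supports that, and it is the boundary where a second baseline helps most. A reader might also infer that the planned analysis is wrong or biased. It is not: the covariate is measured before randomization and the comparison is unbiased with or without Visit 1.

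**What to change.** Add a sentence to SAP 6.3. For SBP, triglycerides, HDL-C and non-HDL-C at 72 weeks, the response remains change from the last pre-dose value and that value remains a covariate. The Visit 1 value enters as a second continuous covariate in the MMRM, the ANCOVA and, for the hybrid estimand, the imputation model. A missing Visit 1 value is filled with the Visit 3 value. State that the same rule applies after a screening pause, since Protocol 10.10 allows up to 90 days between the two visits. Do not replace the Visit 3 covariate with the two-visit mean.

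The change must be pre-specified before unblinding. It needs no new visit or sample and leaves the change-from-randomization endpoint and the linear-model estimand as they are. Protocol 9.4.1 requires an amendment only when a principal feature changes, so this can reasonably be made in the SAP. The downside is one extra term in the analysis model and one in the imputation model.

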8.2.4.1. Immunogenicity Assessment

Where local regulations and ERBs allow, blood samples for immunogenicity testing will be collected to determine antibody production against tirzepatide as specified in the Schedule of Activities (Section 1.3).

At the visits and times specified in the Schedule of Activities (Section 1.3), venous blood samples will be collected to determine antibody production against tirzepatide. To interpret the results of immunogenicity, a PK sample will be collected at the same time points as the immunogenicity sample. All samples for immunogenicity should be taken predose when applicable and possible. In the event of systemic drug-hypersensitivity reactions (immediate or nonimmediate), additional samples will be collected (including antidrug antibodies [ADAs], PK, and exploratory biomarker samples) as close to the onset of the event as possible, at the resolution of the event, and 30 days following the event. Instructions for the collection and handling of blood samples will be provided by the Sponsor. The actual date and time (24-hour clock time) of each sampling will be recorded. Immunogenicity will be assessed by a validated assay designed to detect ADAs in the presence of tirzepatide at a laboratory approved by the Sponsor. Antibodies may be further characterized and/or evaluated for their ability to neutralize the activity of tirzepatide. Sample collected at Visit 801 or Visit 802 will assess immunogenicity at washout of tirzepatide (5 half-lives post end of treatment).

Samples with tirzepatide ADA detected will be titered and evaluated for their ability to neutralize the activity of assigned treatment (tirzepatide-neutralizing antibodies). Samples with tirzepatide ADA detected will also be tested for cross-reactive binding to native GIP and GLP-1, and if such is detected, then for neutralizing antibodies against native GIP and GLP-1, respectively.

Treatment-emergent ADAs are defined in Section 9.4.6.

Samples will be retained for a maximum of 15 years after the last participant visit, or for a shorter period if local regulations and ERBs allow, at a facility selected by the Sponsor. The duration allows the Sponsor to respond to future regulatory requests related to tirzepatide. Any samples remaining after 15 years will be destroyed.

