6.1. Populations for Analyses

For purposes of analyses, [Table GPHK.6.1](#) defines the analysis sets.

Table GPHK.6.1. Description of Analysis Datasets

Analysis Set	Description
Entered Participants	All participants who sign informed consent
Randomized Participants	All participants who are randomly assigned a study treatment
Modified Intent-to-Treat (mITT)	All randomly assigned participants who are exposed to at least 1 dose of study drug. Participants will be included in the treatment group they were randomized to.
Efficacy Analysis Set (EAS)	Data obtained during treatment period from mITT, excluding data after discontinuation of study drug (last dose date + 7 days).
Full Analysis Set (FAS)	Data obtained during treatment period from mITT, regardless of adherence to study drug.
Safety Analysis Set (SS)	Data obtained during the treatment period plus safety follow-up period from mITT, regardless of adherence to study drug.

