Unless otherwise specified, all the analyses listed in this section will be conducted using SS in the following 2 postbaseline periods, respectively:

- up to 72 weeks treatment period plus the safety follow-up (Visit 801, if applicable) for all randomized participants, and
- up to 176 weeks treatment period plus the safety follow-up (Visit 801 or Visit 802) for participants with prediabetes at randomization.

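### The last-postbaseline safety summary for labs, vital signs and ECGs has no end-of-treatment limit, so it mixes on-drug values with off-drug values from Visits 801 and 802

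*SAP*

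**What the plan says.** SAP 6.2, Table GPHK.6.2, row 1.3 covers labs, vital signs and ECGs and is labelled "Change from Last Baseline to Week xx and to Last Postbaseline". Its analysis set is the Safety Analysis Set (SS), which SAP 6.1 defines as "Data obtained during the treatment period plus safety follow-up period from mITT, regardless of adherence to study drug".

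The postbaseline window is borrowed from row 1.2, where "Postbaseline will be defined as measurements after Visit 3". Row 1.3 then adds: "Only scheduled visits will be included. The early discontinuation (ED) visits are considered scheduled visits". Neither row sets a limit at the end of treatment.

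SAP 6.14 gives two safety periods. The first covers everyone randomized and runs to Week 72, with Visit 801 added where it applies. The second is "up to 176 weeks treatment period plus the safety follow-up (Visit 801 or Visit 802) for participants with prediabetes at randomization".

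The protocol's Schedule of Activities lists Visits 801 and 802 as columns of their own. Both collect vital signs, ECG, chemistry, calcitonin, and pancreatic amylase and lipase. Protocol 4.1.1.2.5 says that no study drug is given during safety follow-up. Protocol 8.2.4.1 describes the antibody sample at these visits as taken at washout, five half-lives after treatment ends. Participants with prediabetes who go on past Week 72 do not perform Visit 801.

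**The concern.** A change to the last postbaseline value is normally read as the change at the end of treatment. Here, whoever attends Visit 801 or 802 has that visit as the last scheduled measurement, so the value is taken about 4 or 17 weeks off drug. For a parameter that moves on drug and returns afterwards, the treatment difference in this summary is pulled towards zero.

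The 72-week set has a second problem. Completers without prediabetes contribute a Visit 801 value, while prediabetes participants who continue contribute an on-drug Week 72 value. One mean then combines two drug states in proportions set by prediabetes status and retention.

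The missing limit looks like an omission. Elsewhere the SAP separates the two states: liver enzymes (6.14.3.5.2) and immunogenicity (6.14.3.7) are summarised for the treatment period and for the whole period including follow-up. The maximum QTcF increase (6.14.5) and the MMRM or ANCOVA of selected labs (6.14.6) are tied to the treatment period. Row 1.1 says openly that it includes the off-drug visit. Row 1.3 does none of these.

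**Working it through.** The plan states no figure for this summary, so there is nothing to reproduce. The check asks what share of last values comes from a follow-up visit.

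**Inputs**
- Share with prediabetes, p = 0.60 (Protocol 9.2, planning assumption).
- Dropout to 72 weeks, d = 0.25 (Protocol 9.2).
- Dropout over three years, 0.49, with an annual rate of 22% (Protocol 9.2). These agree: 1 − exp(−0.22 × 3) = 0.483.
- Attendance at Visit 801 or 802 after stopping early is not given. The range runs from no stopper attending to every stopper attending. Completers due a follow-up visit are taken to attend it.
- The planning dropout rates stand in for stopping before the follow-up visit.

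**72-week set**
- Prediabetes participants who continue, last value at Week 72: p(1 − d) = 0.60 × 0.75 = 0.45.
- Low share at Visit 801: (1 − p)(1 − d) = 0.40 × 0.75 = 0.30.
- High share: 0.30 + d = 0.30 + 0.25 = 0.55.
- Over p from 0.50 to 0.70 and d from 0.15 to 0.35, the share runs from about 20% to 68%.

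**176-week set (prediabetes only)**
- Low share at a follow-up visit: 1 − 0.49 = 0.51. High share: 1.00.
- Running the annual rate to 176 weeks gives dropout of 1 − exp(−0.22 × 176/52) = 0.525, which lowers the bottom of the range to 0.475.

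**Drug remaining at these visits**
- Protocol 5.1 equates five half-lives plus 90 days with 4 months. At 30.4 days per month, 4 × 30.4 − 90 = 31.6 days. Taking about 30 days gives an inferred half-life of about 6 days.
- Visit 801 (28 days): 0.5^(28/6) ≈ 0.04. Visit 802 (119 days): effectively zero.
- This is residual drug. It does not show how fast any safety parameter returns to baseline.

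**Dilution, if the effect reverses fully off drug (assumption)**
- Fraction kept = 1 − share. Values not taken at a follow-up visit are treated as carrying the full effect.
- 72-week set: 0.45 to 0.70. For an illustrative 3 bpm difference, 3 × 0.70 = 2.10 and 3 × 0.45 = 1.35. Allowing for the drug left after five half-lives, the lower end is 3 × (0.45 + 0.55 × 2^−5) = 1.40. The result is about 1.4 to 2.1 bpm.
- 176-week set: 1 − 1.00 = 0 to 1 − 0.51 = 0.49, so 0% to 49% is kept.
- Partial reversal dilutes less, in the same direction.

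**With the last value limited to the treatment period**, the share from Visits 801 and 802 is 0% in both sets.

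**The case against.** Four points can be made for the plan as written.

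- **The safety estimand disregards adherence** (Protocol 9.4.4). People who stop drug are asked to keep attending scheduled visits (Protocol 7.1), so a Week 72 value from them would be off drug anyway. This stands. Of the 55 points at the top of the 72-week range, 25 are stoppers. Only the other 30 are on-drug completers whom the rule moves to a washout value, which corresponds to the 2.1 bpm end. It is also a reason to prefer a treatment-period limit to a last-dose limit.
- **On-drug effects are shown elsewhere.** Row 1.3 itself gives change to each week. SAP 6.14.4 to 6.14.6 plan by-visit summaries of vital signs, ECGs and labs. Heart rate has maximum-change and consecutive-visit counts, and pancreatic enzymes have an MMRM and maximum-value thresholds (6.14.3.3.1). This stands: no signal is lost from the study.
- **The term occurs only in Table GPHK.6.2.** SAP 6.14.4 to 6.14.6 describe no such display, and SAP 6.2 says that not every analysis need appear in the study report. This limits the reach to one type of output.
- **The size depends on full reversal**, which the documents do not state, and on a bpm figure chosen for illustration. This stands, so the result is conditional.

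A reader might also infer that the dedicated heart-rate interim is weakened. It is not. That analysis (Protocol 9.5, SAP Appendix 2) uses ambulatory change from Week 0 to Week 36, and the last postbaseline value plays no part in it.

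**Conclusion.** The point holds as a flaw in the definition of one summary. Followed as written, row 1.3 lets off-drug values from Visits 801 and 802 serve as last postbaseline values and mixes them with on-drug values. The share is about 30% to 55% in the 72-week set and about 51% to 100% in the 176-week set, given the planning dropout rates and unknown attendance after stopping.

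Two stronger readings are not supported. One is that most 72-week last values come after washout: 55% is the ceiling, reached only if every stopper attends Visit 801, and prediabetes participants who continue skip that visit. The other is that on-drug effects are erased: this needs full reversal, and in the 176-week set also full attendance at follow-up. The documents establish neither, and other analyses still show the effects.

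No test, adverse-event-of-special-interest rule or trial decision has been shown to depend on this summary. What remains is a possibly diluted endpoint change beside larger by-visit changes, which invites misreading. It is a cheap improvement.

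**What to change.** In Table GPHK.6.2, row 1.3, define last postbaseline as the last scheduled measurement in the treatment period, counting ED visits and excluding Visits 801 and 802. Report the change to Visit 801 or 802 as a separately labelled off-drug summary.

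This keeps off-drug values from participants who stop early but stay in the treatment period, in line with the safety estimand. A last-on-drug version may be added, using the last dose date plus 7 days that the SAP already applies to the Efficacy Analysis Set.

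Leave rows 1.1 and 1.2 unchanged; treatment-emergent events and abnormalities should still cover follow-up.

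The cost is a short SAP edit and one extra table column. No new data are needed.
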